### 9.0 Criteria for Evaluation

CTCAE version 4.03 will be used to assess the grade of mucositis and esophagitis. The principal investigator will train physicians and mid-level providers on the interpretation and grading of mucositis and esophagitis to ensure uniformity and appropriate grading of oral exams.

| Grade             |   |   |   |  |       |  |  |  |  |  |
|-------------------|---|---|---|--|-------|--|--|--|--|--|
| Adverse
Event  | 1   | 2   | 3   | 4  | 5     |  |  |  |  |  |
| Mucositis
Oral | Asymptomatic
or mild
symptoms;
intervention not
indicated | Moderate pain; not
interfering with oral
intake; modified diet
indicated | Severe pain;
interfering with
oral intake | Life-
threatening
consequences;
urgent
intervention
indicated | Death |  |  |  |  |  |

Definition: A disorder characterized by inflammation of the oral mucosal.

For oral mucositis, Grade 3 includes the use of opiates for severe mouth pain, IV fluids needed for decreased oral intake, or hold of mTOR inhibitor-based therapy due to severe mouth pain.

|                  |  | Grade  |  |  |       |  |  |  |  |
|------------------|--|--|--|--|-------|--|--|--|--|
| Adverse
Event | 1  | 2  | 3  | 4  | 5     |  |  |  |  |
| Esophagitis      | Asymptomatic;
clinical or
diagnostic
observations
only;
intervention not
indicated | Symptomatic;
altered
eating/swallowing;
oral supplements
indicated | Severely altered
eating/swallowing;
tube feeding, TPN
or hospitalization
indicated | Life-
threatening
consequences;
urgent
intervention
indicated | Death |  |  |  |  |
| Definition: A    |  | ed by inflammation of t  | he esophageal wall.  | I  | I     |  |  |  |  |

For esophagitis, Grade 2 will be when patients start xyloxylin. Grade 3 is when they start lortab or other narcotics. Grade 3 is defined as feeding tube required secondary to swallowing difficulty rather than uncontrolled nausea.

If patients develop mucositis or esophagitis of grade 1 for more than 5 days or grade 2 or above, the attending physician may have the option to initiate the patient on a best supportive therapy (See Appendix A). The study coordinator or research nurse will record the type and time of treatment of any additional supportive therapy that patients may be given while on the study which will be included in the data analysis.

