The rate of grade three esophagitis ranges between 15-30% in modern studies. The rate seen in most recent NSCLC trial using concurrent chemo/radiation at MD Anderson was 16%. This compares favorable compared to the historic rates of other institutions such as the CALGB 9781 which has a 27% rate. For patients developing Grade 3 esophagitis, radiotherapy can be continued with pain management and IV support, or radiotherapy can be held for </= 5 days until symptoms are < Grade 3.

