## 12.3 Sample Size

There will be a total of 180 patients in this study. The cohort of patients on mTORbased regimens will be 100, and the cohort of patients on radiation regimen will be 80.

For esophagus radiation, published data indicate that the distribution of patients by esophagitis grade is 0-1: 26%, 2: 37%, 3: 37% for patients not given glutamine. If we target a modest treatment effect (0-1: 50%, 2: 38%, 3: 12%) then 40 patients per treatment arm would give us 81% power (assuming a two-sided 5% alpha and use of the Wilcoxon rank sum test for analysis).

For mTOR inhibitor patients, we have unpublished data from 87 patients indicating that the distribution of patients by oral mucositis grade is 0-1: 69%, 2: 22%, 3: 9% for patients not given glutamine. If we target (0-1: 95%, 2: 5%, 3: 0%) as the results in the glutamine arm, then 50 patients per arm would give us 94% power (assuming a two-sided 5% alpha, and use of the Wilcoxon rank sum test for analysis).

These calculations were made using nQuery Advisor 7.0.

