### 12.4 Statistical Analysis Plan

Note: Analyses will be performed separately for patients treated with mTOR inhibitors and patients with esophagus radiation.

For the primary objective, we will use the Wilcoxon rank sum test to compare the ordered categories of mucositis/esophagitis severity between treatment arms. A patient must complete at least 60% of the planned doses of placebo or glutamine to be considered evaluable in the statistical analysis. As a sensitivity analysis for the appropriateness of 60% dosing cut-off, we will analyze the outcome according to the proportion of drug taken. The proportional of drug taken will be computed as the ratio of number of doses taken to the total number of doses prescribed. For the mTOR inhibitor group, the denominator will reflect the total time that each patient is on the study. For the esophagus radiation group, the denominator will reflect the total number of doses that are prescribed during the delivery of radiation.

For the secondary objectives/endpoints, we will compare between treatment arms (1) the trajectories of the mucositis/esophagitis scores over time using linear mixed effects; (2) the proportion of patients developing mucositis/esophagitis using a Pearson chi-squared test; (3) the proportion of patients developing grade 3 or higher mucositis/esophagitis using a Pearson chi-squared test; (4) the duration of mucositis/esophagitis using the Wilcoxon rank sum test; (5) the time to develop mucositis/esophagitis using Kaplan-Meier estimates and the log rank test (due to right censoring in patients not developing mucositis/esophagitis); (6) the proportion of patients having treatment interruptions using a Pearson chi-squared test; (7) the

weight change using the Wilcoxon rank sum test; and (8) the QOL survey scores using the Wilcoxon rank sum test.

For the secondary objective of describing the toxicity profile, descriptive statistics will be provided on the grade and type of toxicity by treatment arm.

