### 12.5 Randomization and Blinding

Patients will be equally randomized between treatment arms using permuted blocks within strata separately for the two groups of patients. For patients who will receive mTOR inhibitor based therapy, randomization will be stratified by: prior mucositis (Y/N), and prior radiation therapy to the head and neck (Y/N). For patients who will

receive radiation to the esophagus, randomization will be stratified based on the volume of esophagus receiving 40 Gy: (1) 20-40%; (2) 41-60%; (3) 61-80%.

CORe will set up a Randomization website and the Investigational Pharmacy personnel will perform the randomization assignment.

Both patients and the research staff conducting the assessment will be blinded to the treatment assignment. Placebo powder identical to glutamine powder in appearance and taste will be compounded by Healios Nutrition Oncology, and both will be dispensed by Investigational Pharmacy at MD Anderson. At the end of the blinded phase, we will assess blinding by asking patients which study arm they believe they have been randomized to.

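### Esophagitis grade 3, a category of the primary endpoint, rests on three criteria with no rule for combining them, and the narcotic criterion has no written indication

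*Combined protocol and SAP*

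**What the plan says.** Section 9.0 names CTCAE version 4.03 as the grading standard and prints its esophagitis row. There, grade 3 means severely altered eating or swallowing, with tube feeding, TPN or hospitalization indicated. Below the table, a paragraph for esophagitis ties grade 2 to the start of xyloxylin and continues: "Grade 3 is when they start lortab or other narcotics. Grade 3 is defined as feeding tube required secondary to swallowing difficulty". The last sentence goes on to exclude tubes needed for uncontrolled nausea.

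The oral mucositis rule in the same section is worded differently: "Grade 3 includes the use of opiates for severe mouth pain", followed by two further criteria joined by an or.

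The grade is used twice. Section 12.2 takes the highest esophagitis grade by week six as the primary endpoint for the radiation cohort, and 12.4 compares the ordered categories with the Wilcoxon rank sum test. Section 12.4 also lists "the proportion of patients developing grade 3 or higher mucositis/esophagitis using a Pearson chi-squared test".

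Three safeguards bear on this:
- Section 9.0 plans training: "The principal investigator will train physicians and mid-level providers on the interpretation and grading of mucositis and esophagitis to ensure uniformity".
- Section 12.5 says patients and "research staff conducting the assessment will be blinded to the treatment assignment".
- Staff record the type and time of added supportive therapy (9.0), and concomitant medications are reviewed weekly during radiation (5.3.3, 6.2).

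**The concern.** There are two gaps. First, nothing says whether the three criteria are alternatives, joint conditions or replacements for one another, and the verb in the tube sentence reads as an exclusive definition. Two trained, blinded graders could therefore put the same narcotic-only patient in different categories of the primary endpoint. Second, the narcotic sentence names no indication, so on its literal terms a narcotic started for pain elsewhere makes the patient grade 3. The mucositis rule closes that gap by tying opiates to mouth pain.

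At stake is dilution of the treatment comparison. Grade 3 scores unrelated to the esophagus would arise in both arms and pull the two distributions together. If the reason for a narcotic is not recorded, attribution may not be recoverable at analysis, and the choice of reading could then be made with the data in hand.

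**Working it through.** **1. The criteria side by side.** Grade 3 or not, by sentence:

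| Patient | CTCAE row | Narcotic sentence | Tube sentence |
|---|---|---|---|
| Narcotic for esophageal pain, no tube | depends on swallowing | yes | no |
| Narcotic for other pain, mild esophagitis | no | yes, literally | no |
| TPN or hospitalization indicated, no tube or narcotic | yes | no | no |
| Tube for swallowing difficulty, no narcotic | yes | no | yes |

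The sentences disagree in every row, and no text resolves the disagreement.

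**2. Reproduce the planned power.** Inputs from 12.3, for grades 0-1 / 2 / 3: control p = (0.26, 0.37, 0.37), glutamine q = (0.50, 0.38, 0.12), n = 40 per arm, two-sided 5%, Wilcoxon.

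- Probability that a control patient has the worse grade, ties counted half: θ = 0.26×0.25 + 0.37×0.69 + 0.37×0.94 = 0.668.
- Null SE, tie-corrected, with mean proportions (0.38, 0.375, 0.245): √[(1 − 0.1223)/12 × 2/40] = 0.0605.
- SE under the alternative: √[(0.0730 + 0.0533)/40] = 0.0562.
- Power = Φ[(0.1681 − 1.96×0.0605)/0.0562] = Φ(0.88) = 81.1%.

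This agrees with the stated 81%. Simulating the tie-corrected test (400,000 trials) also gives 81.1%, with 5.0% rejection under the null.

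**3. Unrelated narcotic starts.** Assume a share s of patients below grade 3, equal in both arms, is scored grade 3. Grades 0-1 and 2 are multiplied by (1 − s). Grade 3 becomes 0.37 + 0.63s in control and 0.12 + 0.88s in glutamine, so the grade 3 gap shrinks from 0.25 to 0.25(1 − s). The share s is an assumption; the documents give no rate.

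| s | Patients moved (control / glutamine, of 40) | Grade 3 (control / glutamine) | θ | Power, formula | Power, simulated |
|---|---|---|---|---|---|
| 0 | 0 / 0 | 0.370 / 0.120 | 0.668 | 81.1% | 81.1% |
| 2% | 0.5 / 0.7 | 0.383 / 0.138 | 0.664 | 78.8% | 78.9% |
| 5% | 1.3 / 1.8 | 0.402 / 0.164 | 0.658 | 75.1% | 75.2% |
| 10% | 2.5 / 3.5 | 0.433 / 0.208 | 0.647 | 68.7% | 69.0% |
| 20% | 5.0 / 7.0 | 0.496 / 0.296 | 0.628 | 55.9% | 56.3% |

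Type I error of the Wilcoxon test stays at 5.0% throughout. For the secondary grade 3 or higher chi-squared test, the same 12.3 distributions give 76% power at s = 0, 67% at 5% and 58% at 10%. The plan states no power target for that test.

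**4. What is not quantified.** A figure for the narcotic-only patient scored two ways would need the share of grade 3 patients with no tube and the grading rule behind the 12.3 control distribution. Neither is in the documents.

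**The case against.** The best defence is that a coherent reading exists. The paragraph opens by limiting itself to esophagitis and reads as a treatment ladder, from xyloxylin at grade 2 to narcotics at grade 3. The nausea clause suggests that the tube sentence only clarifies attribution of the tube element in the CTCAE row. Read as exclusive, it would cancel the narcotic sentence just before it, together with TPN and hospitalization. Letting any one criterion suffice keeps every sentence in force. The xyloxylin sentence has no indication either. A narcotic start plausibly excludes opioids already in use, graders are trained and blinded, and drug starts are logged.

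Much of this stands. The any-of reading is probably what was meant, and the esophagitis context lowers the risk of literal scoring. But the reading is not written, and it would not settle attribution: under any-of, an unrelated narcotic start still qualifies on its face. Training needs a written rule to teach. Blinding makes errors similar between arms but does not prevent them. The logs identify and time a narcotic, but no section asks why it was started; section 7.0 mentions only medications for mucositis.

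A reader might also infer that the spread of grade 3 rates proves inconsistent grading. Section 2.1.2 says "The rate of grade three esophagitis ranges between 15-30% in modern studies" and "The rate seen in most recent NSCLC trial using concurrent chemo/radiation at MD Anderson was 16"%, and cites 27% elsewhere, while 12.3 assumes "the distribution of patients by esophagitis grade is 0-1: 26%, 2: 37%, 3: 37% for patients not given glutamine". The documents do not support that inference. The figures come from different trials, including one in esophageal cancer and one in NSCLC, so differences are to be expected, and no misclassification rate should be derived from them.

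**Conclusion.** The point holds as a gap in the definition of an endpoint category and should be fixed. The text is certain; the size is not. Power falls from 81% to about 79, 75, 69 or 56% if 2, 5, 10 or 20% of patients below grade 3 are misscored equally in both arms. At the low end the loss is small. These figures rest on the 12.3 distributions and on assumed shares.

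Three stronger conclusions do not follow:
- The sample-size arithmetic is not wrong; the 81% reproduces.
- The documents give no ground for expecting bias between arms or an inflated type I error, because assessment is blinded.
- The week-six cut in 12.2 is not an error, although a reader might infer one because later grades are scheduled. A fixed window is legitimate. Week six is most naturally a week of radiation, as are this cohort's other on-treatment week numbers. The 1-month grade falls outside it for essentially every patient, not just in long courses: even 45 Gy at 2.4 Gy takes 19 fractions, ending near day 25, so a visit one month later less 7 days falls in about week 7. The secondary analyses in 12.4 carry no week-six limit.

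**What to change.** In section 9.0, for endpoint scoring:

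- Reconcile the CTCAE row, the narcotic sentence and the tube sentence by stating how they combine.
- Count a narcotic start only when it is attributed to esophagitis, parallel to the mouth-pain condition in the mucositis rule.
- Record the reason for each narcotic start in one field.
- Use the written rule in the planned grader training.

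This concerns scoring only and leaves prescribing to the treating physician. The cost is protocol wording and one data field. The drawback is that 12.3 does not say which grading rule produced its control distribution, so the clarified rule may differ from it and the control proportions may shift.

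Optionally, 12.2 could say that week six means week six of radiation, and a sensitivity analysis could repeat the Wilcoxon test on the highest grade through the 1-month visit. Those grades are already scheduled, though 6.2 allows the 1-month grade to be taken by phone.

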# 4.0 Patient Eligibility

# 4.1 Inclusion Criteria

- Patients who will be initiating therapy with any investigator-initiated mTOR inhibitor based therapy in the Department of Investigational Cancer Therapeutics (Phase I Program) or initiating radiation therapy to the esophagus.
- For the esophagitis arm, any patient with thoracic malignancies, which will receive radiation alone or concurrent chemo/radiation. Radiation dose must be ≥ 45 Gy. For the esophagitis arm, induction chemotherapy is allowed.
- Ability to understand and the willingness to sign a written informed consent. A signed informed consent must be obtained prior to any study specific procedures.
- 4) Patients must be >/= 17 years of age.
- 5) Women of child-bearing potential MUST have a negative serum or urine pregnancy test unless prior hysterectomy or menopause (defined as 12 consecutive months without menstrual activity). Patients should not become pregnant or breastfeed while on this study. Sexually active patients must agree to use contraception prior to study entry, for the duration of study participation, and for 30 days after the last dose.

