# 4.2 Exclusion Criteria

1) Patients currently receiving therapy for mucositis.

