# 5.3.2 Pretreatment Evaluations:

To be completed within 4 weeks prior to initiation of therapy:

- Medical history including list of current concomitant medications and history of mucositis and esophagitis with prior therapy (mucositis and esophagitis history may be obtained by retrospective medical record review).
- Examination of oral mucosa.
- Informed consent
- Weight
- ALC (absolute lymphocyte count)
- Quality of life Questionnaire: MDASI-HN for all patients.
- Medical photograph of oral mucosa for patients receiving therapy with an mTOR inhibitor containing regimen. Attempts to perform medical photographs will be made at this timepoint, but if unsuccessful, will not be considered a deviation to the protocol since it is not a safety assessment.
- Women of childbearing potential will have a pregnancy test using urine and/or blood, and periodically as clinically indicated

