# 7.0 Concomitant medications

Concomitant medications that are being used to treat mucositis will be recorded at each visit.

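### Esophagitis grade 3 is triggered by starting a narcotic, with no stated cause and no rule for patients already on narcotics at entry, so the radiation primary endpoint can misgrade some of them

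*Combined protocol and SAP*

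**What the plan says.** Section 9.0 makes CTCAE the base scale: "CTCAE version 4.03 will be used to assess the grade of mucositis and esophagitis". Its esophagitis row puts severely altered eating or swallowing, tube feeding, TPN and hospitalisation at grade 3. Below the table the protocol adds its own rules for esophagitis. Starting xyloxylin sets grade 2. For grade 3 there are two sentences: "Grade 3 is when they start lortab or other narcotics" and "Grade 3 is defined as feeding tube required secondary to swallowing difficulty rather than uncontrolled nausea".

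The oral mucositis rule in the same section is worded as use and names a cause: "Grade 3 includes the use of opiates for severe mouth pain".

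Eligibility does not touch analgesics. Section 4.1 reads "For the esophagitis arm, any patient with thoracic malignancies, which will receive radiation alone or concurrent chemo/radiation", with a minimum radiation dose and induction chemotherapy allowed. The one exclusion in Section 4.2 is "Patients currently receiving therapy for mucositis".

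On medication data, Section 5.3.2 requires at baseline "Medical history including list of current concomitant medications". Sections 5.3.3 and 6.2 schedule medication reviews weekly during radiation and at 1 and 6 months afterwards. Section 7.0 says "Concomitant medications that are being used to treat mucositis will be recorded at each visit". Section 9.0 also has staff log the type and time of added supportive therapy for use in the analysis.

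Section 12.2 takes the highest esophagitis grade by week six as the primary endpoint. Section 12.3 powers it with grade 3 as the top of three ordered categories.

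**The concern.** A criterion worded as a start is clear for a patient taking no narcotic at entry. It is not clear for one already on a narcotic for tumour or other pain, and nothing in the documents says how to apply it. Two readings are open:

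- **Literal.** The narcotic was not started on study, so the criterion is not met, even if narcotic need later rises because of esophagitis. A patient with no other route to grade 3 stays at grade 2.
- **Being on a narcotic counts.** The same patient is grade 3 from the first week, with or without esophagitis. On the three-level scale a true 0-1 patient moves two categories.

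The missing cause makes this worse, because nothing ties the narcotic to swallowing pain. The mucositis rule shows that the plan could have made that link. At stake is the top category of a primary endpoint in a cohort of 80 with 81% planned power.

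**Working it through.** **Inputs.** From Section 12.3: control 26% / 37% / 37% and glutamine 50% / 38% / 12% for grades 0-1 / 2 / 3; 40 per arm; two-sided 5% alpha; Wilcoxon rank sum test; stated power 81%. Assumed, because the documents give no figure: a share f of patients on narcotics at entry, the same in both arms and unrelated to true grade, shown for 10% to 40%.

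**1. The plan's own figure.** The chance that a control patient has the worse grade, counting ties as half, is

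0.26 × 0.25 + 0.37 × (0.50 + 0.19) + 0.37 × (0.88 + 0.06) = 0.0650 + 0.2553 + 0.3478 = 0.6681.

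The pooled proportions are 0.38, 0.375 and 0.245. The tie factor is 1 − (0.38³ + 0.375³ + 0.245³) = 0.8777. The tie-corrected normal approximation gives

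Φ(0.1681 × √(6 × 40 / 0.8777) − 1.96) = Φ(0.82) = 79.4%.

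Simulating the tie-corrected test (40,000 runs) gives 81.3%. The stated 81% reproduces.

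**2. Literal reading, worst case.** Every baseline user who would be grade 3 is held at grade 2, so in each arm f × (grade 3 proportion) moves from grade 3 to grade 2. At f = 40%:

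- control grade 3: 0.37 × 0.6 = 0.222; grade 2: 0.37 + 0.148 = 0.518
- glutamine grade 3: 0.12 × 0.6 = 0.072; grade 2: 0.38 + 0.048 = 0.428

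The grade 3 difference shrinks from 25 to 15 percentage points.

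**3. Being on a narcotic counts as grade 3.** Each arm's distribution is multiplied by (1 − f), and f is added to grade 3. At f = 40%:

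- control: 0.156 / 0.222 / 0.622
- glutamine: 0.300 / 0.228 / 0.472

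**4. Simulated power, 40 per arm:**

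| Assumed share f | Literal reading, worst case | On a narcotic = grade 3 |
|---|---|---|
| 0% | 81.3% | 81.3% |
| 10% | 79.3% | 69.3% |
| 20% | 77.3% | 56.4% |
| 30% | 75.2% | 44.6% |
| 40% | 73.1% | 34.2% |

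The approximation in step 1 agrees at f = 40%: 71.3% on the literal reading and 34.3% on the other.

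**5. What the table leaves out.** The literal column treats narcotics as the only route to grade 3. Any baseline user who reaches grade 3 through the CTCAE row or the feeding-tube sentence is graded correctly, so the column bounds the loss for a given f. Neither column covers narcotics started on study for pain unrelated to the esophagus, which the missing cause also allows to be scored grade 3.

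**The case against.** The strongest reply is that this is an ambiguity of wording with a small effect. Several parts of it stand.

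- A reader might infer that a baseline user can never be graded 3. The documents do not support that. The CTCAE row and the feeding-tube sentence stay open, and a newly added narcotic may itself count as a start. Only patients whose sole route would be narcotic need are at risk.
- A reader might infer from Section 7.0 that baseline users cannot be identified in the data. That is also unsupported. Section 7.0 does not limit recording to mucositis drugs. The screening list, the unrestricted weekly reviews and the supportive-therapy log can show who was on a narcotic and when one was added. What is unspecified is the reason for use.
- The second reading fits the word *start* less well. It would also make a patient with tumour pain grade 3 at the screening assessment in Section 6.2, before any radiation. Its large losses should not be the headline.
- Assessors are blinded and allocation is random. If glutamine has no effect, the rule acts alike in both arms, so type I error is not inflated. Baseline narcotic use is not a stratification factor in Section 12.5, so chance imbalance is possible.

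Grader training under Section 9.0 does not close the gap, because there is no written rule on this point to train to.

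**Conclusion.** The gap is real and limited. Section 9.0 gives no cause for the narcotic criterion and no rule for eligible patients already on narcotics, so it can misgrade some of them on the primary endpoint. The expected harm is dilution of the treatment effect, not bias towards one arm.

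At an assumed 10-40% share, the literal reading costs at most about 2 to 8 points of power (81.3% to 79.3-73.1%). That rests on the plan's own distributions, narcotic use unrelated to true grade, and affected patients being held at grade 2. The 69-34% range applies only if graders adopt the less natural reading throughout. It shows what inconsistent grading could cost and is not a forecast. The real share is unknown, so the actual loss cannot be derived from the documents.

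**What to change.** In Section 9.0, score the esophagitis narcotic criterion as a new start or an increase relative to the use recorded at screening, attributed by the blinded assessor to esophagitis or swallowing pain. State that narcotic use already present at entry for another reason sets no grade by itself, and that the CTCAE row and the feeding-tube sentence still apply as separate routes to grade 3. Put what counts as an increase into the grader training, so that it is applied uniformly.

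Add a reason-for-use field for narcotics at the screening and weekly concomitant-medication reviews, and align Section 7.0 with it. In Section 12.4, add a sensitivity analysis of the primary endpoint by baseline narcotic use.

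The cost is a few sentences and one data field at reviews that already take place. The small downside is a blinded judgement about why a narcotic was started or increased, which can itself vary between graders. The change governs scoring only and does not concern how pain is treated.
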